## **Appendix C: Adverse Event Reporting and Unanticipated Events**

As noted in section 11, investigators will report all “serious adverse events,” defined as adverse events that are serious and have a reasonable possibility that the event was due to a study drug or procedure (or of uncertain relatedness), to the VCC within 24 hours. The VCC will then notify the single Institutional Review Board (sIRB).

The National/Lead Investigator at the VCC will work collaboratively with the reporting investigator to determine if a serious adverse event has a reasonable possibility of having been caused by the study drug or study procedure, as outlined in 21 CFR 312.32(a)(1), and below. The CC unblinded statistician will also determine if the event is unexpected for lopinavir/ritonavir. An adverse is considered “unexpected” if it is not listed in the investigator brochure or the study protocol (21 CFR 312.32(a)). If a determination is made that a serious adverse event has a reasonable possibility of having been caused by a study procedure or the study drug, it will be classified as a suspected adverse reaction. If the suspected adverse reaction is unexpected, it will be classified as a serious unexpected suspected adverse reaction (SUSAR).

To enhance safety monitoring, the VCC will report every death by coded group (and potentially unblinded group upon request) to the DSMB. The VCC will also report all unexpected deaths, serious and treatment related adverse events, and SUSARs to the DSMB, and sIRB within 7 days after receipt of the report from a clinical site. A written report will be sent to the DSMB and the sIRB within 15 calendar days. The DSMB will also review all reported adverse events and clinical outcomes during scheduled interim analyses. The VCC will distribute the written summary of the DSMB’s periodic review of reported adverse events to the sIRB. The VCC will provide to AbbVie Pharmacovigilance any safety findings for lopinavir/ritonavir (without disclosing protected health information) during the conduct of the trial per contractual language.

### **C.1. Unanticipated Problems (UP)**

Investigators must also report Unanticipated Problems, regardless of severity, associated with study procedures within 24 hours. An unanticipated problem is defined as follows: any incident, experience, or outcome that meets all of the following criteria:

- Unexpected, in terms of nature, severity, or frequency, given the research procedures that are described in the protocol-related documents, such as the IRB-approved research protocol and informed consent document; and the characteristics of the subject population being studied.
- Related or possibly related to participation in the research, in this guidance document, possibly related means there is a reasonable possibility that the incident, experience, or outcome may have been caused by the procedures involved in the research.
- Suggests that the research places subjects or others at a greater risk of harm (including physical, psychological, economic, or social harm) than was previously known or recognized.

### **C.2. Determining Relationship of Adverse Events to Study Drug or Study Procedures**

Investigators will be asked to grade the strength of the relationship of an adverse event to study drug or study procedures as follows:

- Definitely Related: The event follows: a) A reasonable, temporal sequence from a study procedure; and b) Cannot be explained by the known characteristics of the patient’s clinical state

or other therapies; and c) Evaluation of the patient's clinical state indicates to the investigator that the experience is definitely related to study procedures.

- Probably or Possibly Related: The event should be assessed following the same criteria for "Definitely Associated". If in the investigator's opinion at least one or more of the criteria are not present, then "probably" or "possibly" associated should be selected.
- Probably Not Related: The event occurred while the patient was on the study but can reasonably be explained by the known characteristics of the patient's clinical state or other therapies.
- Definitely Not Related: The event is definitely produced by the patient's clinical state or by other modes of therapy administered to the patient.
- Uncertain Relationship: The event does not meet any of the criteria previously outlined.

[figure not shown]
### **C.3. Clinical Outcomes that may be Exempt from Adverse Event Reporting**

Study-specific outcomes of acute respiratory infection, COVID-19, and critical illness will be systematically collected for all patients in both study group and are exempt from adverse event reporting unless the investigator considers the event to be Definitely or Possibly Related (or of an Uncertain Relationship) to the study drug or study procedures. Examples of study-specific clinical outcomes include:

- Death not related to the study procedures.
- Neurological events
  - Seizure
- Cardiovascular events
  - Receipt of vasopressors
  - Atrial or ventricular arrhythmia
  - Cardiac arrest
- Respiratory events
  - Hypoxemia requiring supplemental oxygen
  - Acute respiratory distress syndrome
  - Receipt of mechanical ventilation
  - Receipt of extra-corporeal membrane oxygenation
- Gastrointestinal events
  - Elevation of aspartate aminotransferase or alanine aminotransferase
  - Acute pancreatitis
- Renal events
  - Acute kidney injury
  - Receipt of renal replacement therapy
- Endocrine events
  - Symptomatic hypoglycemia
- Hematologic or coagulation events
  - Neutropenia, lymphopenia, anemia, or thrombocytopenia
- Dermatologic events
  - Severe dermatologic reaction (e.g., Steven's Johnson Syndrome)

Note: A study-specific clinical outcome may also qualify as a reportable adverse event. For example, a ventricular arrhythmia that the investigator considers Definitely or Possibly Related to the study drug would be both recorded as a study-specific clinical outcome and reported as a Serious and Definitely or Possibly Related Adverse Event.

11	Safety Analyses	17
11.1	Adverse Events, Serious Adverse Events, and other Events	17
12	Reporting Conventions	17
13	References	18

3 Abbreviations and Definitions

ACE-I	Angiotensin-converting-enzyme inhibitor
ARB	Angiotensin II receptor blocker
ADR	Adverse drug reaction
ACE	Angiotensin-converting enzyme
AE	Adverse event
ALT	Alanine aminotransferase
AR	Adaptive randomization
ARDS	Acute respiratory distress syndrome
AST	Aspartate aminotransferase
AUC	Area under the curve
BAL	Bronchoalveolar lavage
BID	“Bis in die” (twice daily)
CC	Coordinating Center
CFR	Code of Federal Regulations
COVID-19	Coronavirus Disease 2019
CYP3A	Cytochrome P4503A
DCC	Data Coordinating Center
DSMB	Data and safety monitoring board
ECMO	Extracorporeal membrane oxygenation
eCRF	Electronic case report form
EKG	Electrocardiogram
FDA	Food & Drug Administration
GFR	Glomerular filtration rate
HIPAA	Health Insurance Portability and Accountability Act
HIV	Human immunodeficiency virus
HR	Hazard ratio
IC ₅₀	Half maximal inhibitory concentration
ICU	Intensive care unit
ID	Identification
IL1	Interleukin-1
IL6	Interleukin-6
IP	Investigational product
IRB	Institutional Review Board
IRIS	Immune reconstitution inflammatory syndrome
IV	Intravenous
IVY Network	Influenza Vaccine Effectiveness in the Critically Ill Network
KDIGO	Kidney Disease Improving Global Outcomes
LFT	Liver function test

LPV/r	Lopinavir/ritonavir
MERS-CoV	Middle East respiratory syndrome coronavirus 2
MIC	Minimum inhibitory concentration
NHLBI	National Heart, Lung, and Blood Institute
NIH	National Institutes of Health
NSAIDs	Nonsteroidal anti-inflammatory drug
pH	Potential for hydrogen
PI	Principal investigator (a clinician responsible for one site)
PK/PD	Pharmacokinetics/pharmacodynamics
PPE	Personal protective equipment
PPoS	Predictive probability of success
QD	“quaque die” (once daily)
QID	“quater in die” (four times daily)
QR code	Quick response code
QTc	QT interval corrected for heart rate
RCT	Randomized control trial
REDCap	Research Electronic Data Capture
RT-PCR	Reverse transcription polymerase chain reaction
SAE	Serious adverse events
SARS-CoV-2	Severe acute respiratory syndrome coronavirus 2
S/F	SpO ₂ /FiO ₂ ratio
sIRB	Single IRB
SOFA	Sequential Organ Failure Assessment
SUSAR	Suspected unexpected serious adverse reaction
US	United States
VAS	Visual Analog Scale

4 Introduction

4.1 Preface

Effective therapies for COVID-19 are urgently needed. Lopinavir/ritonavir (Kaletra), an antimicrobial agent used to treat HIV-1, has demonstrated in vitro inhibition of SARS-CoV-2, the virus that causes COVID-19. Initial clinical data have suggested possible relevance as a therapeutic agent when administered early in the disease course of patients with COVID-19. The TREAT NOW study was designed to test the hypothesis that lopinavir/ritonavir reduces disease progression and improves clinical status measured using a seven point at day 15 following receipt of study drug when compared with placebo. The TREAT NOW study is a multicenter, blinded, non-matching placebo-controlled, randomized clinical trial to evaluate the superiority of active therapy (lopinavir/ritonavir) versus placebo control. Briefly, patients testing positive for SARS-CoV-2 infection in an outpatient setting are contacted by research coordinators and invited to participate. Adults with a positive SARS-CoV-2 test are either self-referred or identified via review of testing records at participating sites. Patients who are still symptomatic and who are within six days of symptom onset are invited to participate. Eligible participants who provide their consent to participate using an electronic system undergo comprehensive baseline data collection via phone survey, the participant is randomized, and study drug or placebo is shipped overnight to the participant's home. The participant then completes a daily web-based medication adherence, symptom burden, and hospitalization survey for sixteen days. Missed surveys result in telephone follow up to complete missing data and to re-engage the participant in completing the study. At day 15, the primary outcome is assessed. Patients are followed up once more at 29 days

4.2 Scope of this statistical analysis plan

The TREAT NOW clinical protocol was developed to adapt to allow for addition of new agents and changing standards of care. In the absence of any planned adaptations, this document is restricted to the statistical design and analysis of a comparison between two groups of participants: patients randomized to receive lopinavir/ritonavir and patients randomized to receive a placebo. If new agents are introduced for testing, or other adaptations are sought, this document will be revised accordingly.

Section 5 introduces and defines the study objectives and endpoints. Study methods including the overall design, inclusion/exclusion criteria, randomization, and blinding are in Section 6. Sample size justifications are in Section 7. Section 8 discusses the analysis populations and planned interim analyses. Subject disposition, derived variable definitions, and protocol deviations are defined in Section 9. Sections 10 and 11 detail the planned efficacy and safety analyses, respectively. The final sections, after Section 12, note reporting conventions, any updates to the SAP and/or protocol after SAP approval, and references.

5 Study Objectives and Endpoints

5.1 Study Objectives

To determine whether early treatment with lopinavir/ritonavir improves clinical status at 15 days when compared to placebo in outpatient adults with COVID-19. Secondary objectives include describing the safety profile of lopinavir/ritonavir, and to determine whether the clinical progression is improved through to Day 29.

5.2 Treatment arms

The active treatment arm of lopinavir/ritonavir (LPV/r) consists of standard dosing with 400mg/100mg taken orally twice daily for 28 doses. Medication dose packs contain all 28 doses labelled by study day. The LPV/r dosing is based upon extensive PK/PD study evaluations in healthy and HIV+ subjects.

The control arm consists of unmatched placebo taken orally twice daily for a total of 28 doses. Medication dose packs will contain all 28 doses labelled by study day. Given the unmatched placebo pill to LPV/r, exclusion will be exercised to ensure two individuals from the same household are not enrolled in the study and that telephone assessments during the study avoid discussion of the appearance of the study medication.

5.3 Endpoints/Outcomes

In this section endpoints/outcomes are described with how they should be operationalized for analysis. Additional information on the study population(s) are defined in Section 8.2 with respect to those included for analysis. Per the protocol, timing of study procedures is based on the time of randomization, which is defined as Baseline. Study Day 1 is defined as the day of receipt of the first dose of the study drug.

Primary outcome:

The primary outcome is the daily status based on the proposed Modified COVID Ordinal Outcomes Scale from Study Day 1 through Study Day 15:

1. Death
2. Hospitalized on mechanical ventilation or ECMO
3. Hospitalized on supplemental oxygen
4. Hospitalized not on supplemental oxygen
5. Not hospitalized with symptoms and limitation in activity
6. Not hospitalized with symptoms but with no limitation in activity
7. Not hospitalized without symptoms nor limitation in activity

Each daily status is derived primarily from the daily study survey through day 16 after randomization and the chart review on day 29 after randomization. This is a longitudinal measure of the ordinal outcome from receipt of study medication (Study Day 1) to completion of study treatment (Study Day 15).

Secondary outcomes:

The secondary outcomes are described below with details on operationalization:

- Modified COVID Ordinal Outcome Scale on Study Day 8
 - The ordinal outcome of the previously defined scale on Study Day 8 after one week of treatment.
- Modified COVID Ordinal Outcome Scale on Study Day 15
- Modified COVID Ordinal Outcome Scale on Study Day 29
 - The ordinal outcome of the previously defined scale on Study Day 29 after one month of treatment receipt.
- Proportion of patients hospitalized through Study Day 29
 - A dichotomous indicator if the participant was hospitalized at any point through Study Day 29 as reported on daily surveys or through the Day 29 Chart Review.
- Time to hospitalization through Study Day 29
 - The number of days from receipt of study medication (Study Day 1) to first

hospitalization for any reason through Study Day 29.

- Time to symptom resolution through Study Day 29
 - The number of days from receipt of study medication (Study Day 1) to resolution of all symptoms reported without recurrence. For example, if a participant reports no symptoms on the daily survey on Study Day 5, but then symptoms are reported again on Study Days 6 through 8 with resolution of all symptoms on Study Day 9, the number of days for resolution would be 9 and not 5 to reflect the recurrence of symptoms.
- All-cause, all-location mortality up to Study Day 29
 - A binary variable indicating death for any reason from receipt of study drug (Study Day 1) through Study Day 29.
- Oxygen-free days through Study Day 29
 - The number of days derived from the Modified COVID Ordinal Outcome Scale where there is no reported supplemental oxygen, mechanical ventilation, or ECMO from receipt of study drug (Study Day 1) to Study Day 29 during hospitalization. Death before Study Day 29 will be penalized by using a value of -1 free days.
- Fever-free days through Study Day 29
 - The number of days where fever is reported as "None" versus "Mild", "Moderate", or "Severe" based upon daily surveys between receipt of study drug (Study Day 1) and Study Day 29. Death before Study Day 29 will be penalized by using a value of -1 free days.
- Ventilator-free days through Study Day 29
 - The number of days derived from the Modified COVID Ordinal Outcome Scale where there is no reported mechanical ventilation or ECMO from receipt of study drug (Study Day 1) to Study Day 29. Death before Study Day 29 will be penalized by using a value of -1 free days.
- Vasopressor-free days through Study Day 29
 - The number of days from receipt of study drug (Study Day 1) to Study Day 29 based upon the Study Day 29 Chart Review where no vasopressor use is denoted. Death before Study Day 29 will be penalized by using a value of -1 free days.
- ICU-free days through Study Day 29
 - The number of days from receipt of study drug (Study Day 1) to Study Day 29 based upon the Study Day 29 Chart Review where there is no portion of the day spent in the ICU. Death before Study Day 29 will be penalized by using a value of -1 free days.
- Hospital-free days through Study Day 29
 - The number of days from receipt of study drug (Study Day 1) to Study Day 29 based upon daily surveys and the Study Day 29 Chart Review where there is no portion of the day spent admitted to a hospital setting. Death before Study Day 29 will be penalized by using a value of -1 free days.

Safety outcomes:

Safety outcomes to be included in the safety analysis for this trial include all potentially associated adverse events (PAAEs) as well as other events of interest including, but not necessarily limited to:

- Seizure
- Atrial or ventricular arrhythmia
- Cardiac arrest
- Receipt of renal replacement therapy

- Severe dermatologic reaction
- *Elevation in aspartate aminotransferase or alanine aminotransferase to twice the local upper limit of normal AND at least doubling over known baseline
- *Acute pancreatitis
- *Acute kidney injury by KDIGO criteria
- *Symptomatic hypoglycemia
- *Anemia or thrombocytopenia

* For participants whose symptoms are significant enough to trigger a clinical work-up and thus have clinically available testing

6 Study Methods

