## 6.1 Baseline Variable Collection

- Informed Consent Document and documentation of consent process
- Presence or absence of each inclusion and exclusion criterion
- Date and time of enrollment
- Day of symptom onset
- Specimen type, date, and result of SARS-CoV-2 testing conducted clinically.
- Demographics (age, sex, race, ethnicity, height, weight)
- Comorbidities: chronic cardiac disease, chronic pulmonary disease, chronic kidney disease, chronic liver disease, chronic neurological disease, malignant neoplasm, chronic hematologic disease, AIDS/HIV, obesity, diabetes with complications, diabetes without complications, rheumatologic disorder, malnutrition, smoking, other
- Chronic use of medication: ACE inhibitors, angiotensin receptor blockers
- Receipt of azithromycin in the past week
- Presenting signs and symptoms, along with self-reported severity

## 6.2 Daily Assessments between Randomization and Study Day 16, and then at Day 29

- Study drug administration and reason for missed doses.
- Modified COVID Ordinal Outcomes Scale
- Daily signs and symptoms, along with self-reported severity via electronic log and/or telephone interview.
- Day of symptom resolution
- Receipt of open label antivirals: chloroquine, hydroxychloroquine, remdesivir, lopinavir/ritonavir, other
- Receipt of open label immunomodulators between enrollment and hospital discharge: corticosteroids, tocilizumab, sarilumab, interferon  $\beta$ , other
- Receipt of azithromycin
- Study days in hospital (if applicable)
- Study days receiving supplemental oxygen (if applicable)
- Study days receiving non-invasive or invasive mechanical ventilation (if applicable)
- Study days in ICU to Study Day 29
- Study day of death (if applicable)
- Safety Outcomes: seizure, atrial or ventricular arrhythmia, cardiomyopathy, cardiac arrest, aspartate aminotransferase or alanine aminotransferase levels that are greater than twice the local upper limit of normal (or two times higher than known baseline), acute pancreatitis (defined by a clinically obtained lipase level above the local upper limit of normal and abdominal pain or vomiting), stage II or greater acute kidney injury according to KDIGO criteria, receipt of new renal replacement

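### The SAP's oxygen-free-days rule, read literally, counts only hospital days and scores a never-admitted survivor 0; on any reading its source misses home oxygen

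*SAP*

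**What the plan says.** SAP 5.3, which sets out how each endpoint is to be operationalized, defines oxygen-free days as "The number of days derived from the Modified COVID Ordinal Outcome Scale where there is no reported supplemental oxygen, mechanical ventilation, or ECMO", counted "from receipt of study drug (Study Day 1) to Study Day 29 during hospitalization". It adds: "Death before Study Day 29 will be penalized by using a value of -1 free days".

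Ventilator-free days, in the same list, use the same scale, window and death rule but no hospital restriction: days "where there is no reported mechanical ventilation or ECMO from receipt of study drug (Study Day 1) to Study Day 29".

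The scale itself (SAP 5.3) mentions oxygen at two levels only, both in hospital: level 3, "Hospitalized on supplemental oxygen", and level 4, "Hospitalized not on supplemental oxygen". Level 2 is ventilation or ECMO, also in hospital. Levels 5-7 grade outpatients by symptoms and activity and say nothing about oxygen.

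Protocol 5.2 gives the outcome's name and no definition. Protocol 6 (Electronic Data Collection) has patients asked daily about oxygen requirements, and Protocol 6.2 lists a separate item, "Study days receiving supplemental oxygen (if applicable". SAP 10.2.1 fits an ordinal model to free-day outcomes because of the death penalty.

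**The concern.** In an outpatient trial meant to show less disease progression, the best result on this outcome should be to survive without needing oxygen. On the literal wording that patient scores 0, one step above death, and hospital days off oxygen raise the score. Because the analysis is ordinal, the ranking is what is analysed, so an error in the ranking is an error in the result.

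The wording can also be read the other way, and neither document says how a never-admitted patient is scored. Two programmers could follow the SAP faithfully and produce opposite rankings.

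The second problem is the source. A scale that records oxygen only in hospital cannot count oxygen given at home.

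**Working it through.** The SAP states no figure for this outcome, so there is none to reproduce. The check applies the SAP 5.3 rule to illustrative patient courses.

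**Inputs.** The window is Study Day 1 to Study Day 29, which is 29 - 1 + 1 = 29 days. The scale levels and the death score of -1 are from SAP 5.3. The courses are invented.

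**Two readings.**
- Literal: the phrase limits which days are counted. Score = number of hospital days that are neither level 2 nor level 3 = number of level 4 days.
- Charitable: the phrase describes the oxygen use. Score = 29 minus the number of level 2 and level 3 days.

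| Course over 29 days | Literal | Charitable |
|---|---|---|
| Never admitted, no oxygen | 0 | 29 |
| Never admitted, 10 days of home oxygen | 0 | 29 |
| 5 hospital days, none on oxygen | 5 | 29 |
| 10 hospital days, none on oxygen | 10 | 29 |
| 5 hospital days, all on oxygen | 0 | 29 - 5 = 24 |
| 10 hospital days, all on oxygen | 0 | 29 - 10 = 19 |
| 10 ventilated and 5 oxygen days, then 5 hospital days off oxygen | 5 | 29 - 15 = 14 |
| 10 ventilated and 5 oxygen days, then 10 hospital days off oxygen | 10 | 29 - 15 = 14 |
| Death before Day 29 | -1 | -1 |

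**What follows.**
1. On the literal reading, the never-admitted survivor (0) ties with a patient who spent 10 hospital days entirely on oxygen, and ranks below a patient ventilated for 10 days who then stayed in hospital off oxygen (5 or 10).
2. On the charitable reading the order is sensible for hospital care: 29, then 24 and 19, then 14, then -1.
3. On both readings, 10 days of home oxygen without admission scores the same as no oxygen at all. Counting those days would give 29 - 10 = 19. Deleting the phrase therefore settles the ranking but not the source problem.

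**How many patients are affected.** The documents do not give the share never admitted through Day 29. The SAP section 7 planning table is a single-time status, taken here as Day 15, the day named for the primary comparison in Protocol 7. Levels 5-7 add to 10 + 24 + 55 = 89% on placebo and 6.6 + 18.7 + 68.1 = 93.4% on active treatment. These are ceilings on the planned share alive and never admitted by that day, since they also include patients already discharged. That the never-admitted are a majority is an assumption, consistent with outpatient enrolment and with Protocol 5.4, which expects most to recover without critical illness.

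**The case against.** The strongest reply is that the charitable reading is the natural one. It fits the outcome's name, the -1 for death (which makes sense only if 0 is already a poor result), and the other free-day outcomes, none of which is confined to hospital days. The phrase may only acknowledge that the scale sees oxygen in hospital. This is persuasive about intent, and the point should not be read as showing that the sponsor means to score never-admitted patients 0. But no sentence in either document resolves the wording.

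A reader might go further in three ways that the documents do not support.
- *That the planned benefit would show up as harm*, because levels 2-4 hold 10% of placebo and 6.1% of active patients in the planning table. Level 2 and 3 days cannot count on the literal reading; level 4 alone is 3% against 1.9%. Status on one day is also not ever-admitted status: a patient discharged by Day 15 may have earlier level 4 days. Fewer deaths (1% against 0.6%) would move the score the other way. The ranking fault is shown; its net effect on the comparison is not.
- *That the rule rewards any longer stay.* Only extra hospital days off oxygen add to the score; extra days on oxygen add nothing.
- *That oxygen after Day 16 is lost.* SAP 5.3 and 9.3 use the Day 29 chart review to derive or verify status. That text concerns the primary outcome, but the review could recover later in-hospital oxygen.

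It is also fair to say that the protocol's oxygen-days item follows the same schedule (daily to Day 16, then Day 29) and does not say whether it covers home use. It is a better source, not a complete one.

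**Conclusion.** The definition is wrong as written. Its literal meaning misranks patients, and its probable meaning is not stated. For a survivor never admitted, the readings differ by the full window, 0 against 29. The share of patients affected cannot be taken from the documents.

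Separately, and on either reading, home oxygen is counted as oxygen-free although oxygen data are collected outside the scale. The documents give no frequency for home oxygen, so the size of that error is unknown.

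This is one secondary outcome. It does not enter the primary analysis, the sample size or the numerical stopping thresholds. The correction is worth making because it is nearly free and the present text can yield opposite rankings.

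**What to change.** In SAP 5.3, before unblinding:
- Delete *during hospitalization*. Define the outcome as the number of days, Study Day 1 to Study Day 29 inclusive, with none of supplemental oxygen, ventilation or ECMO, in any setting.
- State that a survivor who never received any of these scores the maximum (29), and keep -1 for death.
- Name the sources: the daily oxygen questions, the separately recorded oxygen days and the Day 29 chart review, in place of the ordinal scale alone.
- State how Days 17-28 are obtained, and that home oxygen may be incompletely captured on those days.

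The cost is SAP wording and the matching program. No new data collection is needed for in-hospital oxygen, provided the chart review records it. For home oxygen, the sponsor should check what the existing forms capture; if they miss Days 17-28, that limitation should be reported with the result.
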